Study protocol

Efficacy and Safety of a Multiple-Action Tear Substitute (TriMix) in Dry Eye Disease: A Randomized, Double-Blinded, HA-controlled Study

Date: June 14, 2024.

1. Study design

This was a randomized, double-masked, HA-controlled clinical trial conducted in the ophthalmology departments of Tedesco Eye Center (Girifalco, CZ, Italy) and Russo multi-specialty medical practice ([name], CZ, Italy) between July, 2023 and May, 2024. The study protocol fulfilled all the requirements of the Declaration of Helsinki. Before initiating the study, informed and written consent was obtained from each patient.

2. Participants

Eligible patients were adults \geq 18 years old with a self-reported history DED while working with computer screens \geq 6 hours per day. Patients had to meet the following inclusion criteria in \geq 1 eye at screening and randomization to be enrolled in the study: (1) ocular surface disease index (OSDI) $>$ 13 points; (2) non-invasive tear film break-up time (NIBUT) $<$ 10 s; (3) Schirmer test (ST) without anesthesia \geq 5 mm and (4) MGD grade \leq 1. For MGD, the Sirius device (CSO, Florence, Italy) was used, which determines MGD grade based on loss area of meibomian glands (LAMG). MGD grade was scored from 0 to 4 (MGD grade 1 = LAMG $<$ 25%; MGD grade 2 = LAMG \geq 25% and $<$ 50%; MGD grade 3 = LAMG \geq 50% and $<$ 75%; MGD grade 4 = LAMG \geq 75%).

Patients were excluded from the study if they met any of the following criteria: (1) abnormal lid anatomy, including active blepharitis, and active lid margin; (2) all corneal disorders that affect diagnostic test, such as active corneal infection and corneal dystrophies; (3) active ocular allergies; (4) vectored thermal pulsation (VTP) intense pulse light (IPL), quantum molecular resonance (QMR), or other procedure to treat DED within the previous 6 months; (5) intraocular surgery or laser ocular surgery within the previous 6 months; (6) use of topical antibiotics and anti-inflammatory treatments, including steroids and non-steroidal anti-inflammatory drugs; (7) systemic autoimmune diseases; (8) contact lens wearers; (9) pregnant or lactating women; (10) patients who did not understand or comprehend the informed consent. Prior use of tear substitutes was allowed, and there was a one-month washout period after enrollment.

3. Randomization, intervention and masking

Eligible participants were randomized in a 1.5:1 ratio to receive either TriMix tear substitute (Off Health S.p.a., Firenze, Italy) or 0.15% HA tear substitute (Thea Pharma S.p.a., Milan, Italy). Randomization tables were generated by an unmasked statistician not otherwise involved in the trial using the software “randomiser” (Appier inc., Taiwan, China). Patients were instructed to instill 1 drop TriMix tear substitute or 0.15% HA tear substitute into each eye 3 times per day for 6 months. HA-based tear substitutes can reduce tear film hyperosmolarity and are effective in treating DED. Therefore, 0.15% HA tear substitute was selected as a suitable comparator. Both tear substitutes are transparent, with no special smell and the bottles were identical in appearance such that patients and investigators were masked to treatment assignment.

4. Clinical outcomes

The study design is shown in Figure 1. Patients were assessed at screening, baseline (day 1), and 2 follow-up visits: 3 months (12 ± 1.5 weeks) and 6 months (24 weeks ± 1). All clinical outcomes were conducted in the order suggested by Ballesteros et al. to maintain the integrity of the tear film. Furthermore, these measurements were taken under consistent environmental conditions in the same room by a trained optometrist.

4.1. Dry eye symptoms

The OSDI questionnaire were employed to assess the severity of DED symptoms, with scores ranging from 0 (indicating no ocular surface disease) to 100 (indicating severe ocular surface disease) points [1,2]. This questionnaire was provided during consultations at each follow-up visit.

4.2. Tear film stability

Tear film stability was automatically assessed using NIBUT by projecting Placido rings from the Sirius device (CSO, Florence, Italy) onto the corneal surface. The time interval between the last blink and the initial distortion of the ring pattern was defined as first NIBUT. This variable was always measured at least 12 hours after administration of the study medication and the average of 3 consecutive measurements was calculated for statistical analysis.

4.3. Tear film volume

Tear film volume was evaluated with unanesthetized ST. During the test, the patient is instructed to look upward while the test strip is carefully positioned between the palpebral conjunctiva of the lower eyelid and the bulbar conjunctiva. Subsequently, the patient is asked to keep their eyes gently closed for five minutes. After this period, the test strip is removed, and the Schirmer test score is determined by measuring the length of the moistened area on the strip.

5. Statistical analysis

Statistical analyses were performed with SPSS statistics software, version 25.0 (IBM Corporation, NY, USA). The sample size was estimated using the GRANMO calculator, version 7.12 (Municipal Institute of Medical Research, Barcelona, Spain). It was calculated based on a statistically significant paired difference of 1.24 ± 2.56 s at 2 months after the TriMix tear substitute treatment onset. This assumed difference was based on the findings of a pilot study with 25 eyes [3]. With these assumptions, a sample size of 40 eyes per group would yield a power $> 80\%$ and a statistically significant paired difference of 95% confidence. A 20% discontinuation rate was considered when calculating sample size. Continuous variables were displayed as the mean \pm standard deviation (SD), while ordinal categorical variables were expressed as frequencies (n) and percentages (%). When both eyes were eligible, the eye with a lower baseline NIBUT was selected for the analyses. If the baseline NIBUT was the same in both eyes, the right eye was selected. Since the Kolmogorov-Smirnov test showed that the clinical endpoints did not meet the normality criteria, nonparametric tests were performed. The Friedman test (non-parametric) was performed to compare intra-group clinical outcomes. Within each group, the increment (Δ) was calculated. It was defined as the change from the last visit (LV) to baseline (B): $D = LV - B$. Inter-group clinical outcomes were analyzed with the Mann-Whitney U test. Between each group, the differences were calculated as $\Delta_{\text{TriMix group}} - \Delta_{\text{HA group}}$. Categorical variables were compared using the χ^2 test. A P value of less than 0.05 is considered to be statistically significant.

References

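### The 40 eyes per group and power above 80% describe a before/after change within TriMix; power for the randomized comparison with HA is not stated

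*Combined protocol and SAP*

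**What the plan says.** All sizing information is in section 5 of the combined protocol and SAP. The size was "calculated based on a statistically significant paired difference of 1.24 ± 2.56 s at 2 months after the TriMix tear substitute treatment onset", an effect taken from a 25-eye pilot. From this, "a sample size of 40 eyes per group would yield a power" above 80% "and a statistically significant paired difference of 95% confidence". Loss is covered by one sentence: "A 20% discontinuation rate was considered when calculating sample size". The variable is not named. The unit is seconds and section 4.2 describes a time ("The time interval between the last blink and the initial distortion of the ring pattern was defined as first NIBUT"), so it is presumably NIBUT.

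Section 5 plans two kinds of comparison:

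- Within each arm: "The Friedman test (non-parametric) was performed to compare intra-group clinical outcomes".
- Between arms: "Inter-group clinical outcomes were analyzed with the Mann-Whitney U test". The increment is last visit minus baseline. "Between each group, the differences were calculated as" introduces the contrast, which is the TriMix increment minus the HA increment.

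Section 3 sets the allocation at 1.5:1, TriMix to HA, and justifies HA as the comparator. Section 4 schedules follow-up at 3 and 6 months. One eye per patient is analysed, so eyes and patients are the same count.

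**The concern.** A trial randomized against an active comparator exists to compare the two arms. The only power figure in the plan concerns something else: whether eyes given TriMix change from their own baseline. That question does not use the HA arm, and a positive answer cannot separate a TriMix effect from change that would have occurred anyway. Regression to the mean is plausible here, because entry requires NIBUT below 10 s and the eye with the lower baseline NIBUT is analysed.

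A reader who meets a per-group size and a power above 80% in an HA-controlled trial may carry the 80% over to the HA comparison. A non-significant TriMix–HA difference could then be taken as evidence of similarity from an adequately powered test. Equally, a significant within-TriMix change could be taken as evidence against HA. The stated figure supports neither.

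**Working it through.** **Inputs from section 5.** Paired change 1.24 s, SD 2.56 s (read as the SD of the change), significance level 0.05 (two-sided assumed, since sidedness is not stated), power 80%, loss 20%, stated size 40 per group.

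**Step 1: reproduce the plan's figure with a paired formula.**

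n = (1.96 + 0.8416)² × (2.56 / 1.24)² = 7.849 × 4.262 = 33.45.

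Allowing for loss: 33.45 × 1.2 = 40.1; dividing by 0.8 instead gives 41.8. The stated 40 is therefore recovered by a paired calculation, most closely with the factor 1.2.

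**Step 2: paired power at the sizes the text allows.** The z version is Φ(1.24 × √n / 2.56 − 1.96); the t version uses the noncentral t distribution.

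| TriMix eyes evaluable | How it arises | Power, t | Power, z |
|---|---|---|---|
| 32 | 40 before loss, less 20% | 76% | 78% |
| 38 | 48 before loss, less 20% | 83% | 85% |
| 40 | 40 completers | 85% | 86.5% |
| 48 | 60 before loss, less 20% | 91% | 92% |

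These are paired t or z figures. The planned within-arm test is a Friedman test over visits, so they are not exactly its power either.

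**Step 3: try a two-sample formula on the same inputs.** With equal arms, no HA change and SD 2.56 s in both arms, n per arm = 2 × 33.45 = 66.9, so 67. At 1.5:1 the HA arm needs (1 + 1/1.5) × 33.45 = 55.8, so 56, with 84 on TriMix. Neither leads to 40.

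**Step 4: illustrate between-group power.** The documents give no HA change, HA SD or total sample size. Assume no HA change, a true difference of 1.24 s, SD 2.56 s in both arms and normal data. The standard error is 2.56 × √(1/n₁ + 1/n₂).

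| TriMix:HA | Basis | SE (s) | 1.24 / SE | Two-sample t power |
|---|---|---|---|---|
| 40:40 | 40 in each arm | 0.572 | 2.17 | 57% |
| 48:32 | 80 in total at 1.5:1 | 0.584 | 2.12 | 55% |
| 60:40 | 40 as the smaller arm | 0.523 | 2.37 | 65% |
| 32:32 | 40:40 less 20% | 0.640 | 1.94 | 48% |
| 38:26 | 48:32 less 20% | 0.652 | 1.90 | 47% |
| 48:32 | 60:40 less 20% | 0.584 | 2.12 | 55% |

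**Step 5: how far the assumptions move this.** An HA SD between 2.0 and 3.0 s gives 47–77% before loss and 39–67% after. Section 5 reports that the endpoints failed a normality check, so the shape of the distribution matters too. In simulations with heavy-tailed t(3) data scaled to SD 2.56 s, Mann-Whitney power for 1.24 s is 80–88% before loss and 72–80% after. No single value can be read from the documents.

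**Step 6: compare the sizing with the design.** The sizing effect is at 2 months; the visits are at 3 and 6 months, and the contrast uses the last visit. The size is given per group, yet the allocation is 1.5:1 and no arm totals appear. The text does not say whether 40 is before or after the 20% loss.

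**The case against.** The strongest defence is that the plan conceals nothing. Section 5 uses the word *paired* twice, never attributes its power to the HA comparison, names no primary endpoint, and already defines and tests the TriMix-minus-HA difference. The paired arithmetic reproduces. This stands as far as it goes: there is no arithmetic error and no explicit false claim. It does not supply the missing power, and a per-group size in an HA-controlled trial invites the wrong reading.

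Several stronger readings are tempting but not supported:

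- *The HA comparison was underpowered.* The 47–65% in Step 4 rests on assumed HA values and normal data; heavy tails can bring Mann-Whitney power to 80% or more.
- *Even the paired power misses 80%.* That holds only if 40 is the TriMix number before loss. It arises from multiplying by 1.2 and then by 0.8, which leaves 32 eyes against the 33.45 required. The other readings in Step 2 give 83–92%.
- *Forty per group contradicts 1.5:1.* Forty could be a minimum per group, as at 60:40. What is missing is the arm sizes.
- *The contrast must be below 1.24 s because HA works.* Section 3 describes HA as effective in dry eye disease but gives no HA effect on NIBUT. The 1.24 s is a 2-month figure, and no 6-month TriMix change is stated.

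Nor do the documents draw any conclusion from within-group p-values; the last part of the fix is a precaution.

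**Conclusion.** The concern holds as a mismatch between the power calculation and the design. The stated size and power come from a one-arm, before/after calculation and do not apply to the randomized TriMix–HA comparison, for which the plan states no difference, HA SD or power. This follows from the text and from Step 1, and depends on no outside assumption beyond a two-sided 0.05 level.

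The illustrative size of the gap is paired power of 85–86.5% at 40 completers, against two-sample t power of about 55–65% before loss and 47–55% after. The between-group figures depend on zero HA change, SD 2.56 s in both arms and normal data, and should not be quoted as the trial's power. The arm sizes, the handling of loss, the sizing variable and the link from a 2-month effect to the 3- and 6-month visits also remain unstated. This is more than missing detail, because the one power figure offered does not address the comparison for which patients were randomized.

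**What to change.** Amend section 5 as follows.

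1. State that the 40-eye figure and power above 80% refer only to the paired change within TriMix at 2 months, name the variable, and state that the comparison with HA was not powered in the plan.
2. Give the arm sizes under 1.5:1 and say whether 40 is before or after the 20% loss. If it is the TriMix number before loss, so that 32 remain, restate the paired power as about 76% (t) to 78% (z).
3. Report the TriMix-minus-HA difference with a 95% confidence interval suited to the Mann-Whitney test, for example a Hodges-Lehmann interval. Base any conclusion about TriMix versus HA on that contrast, not on within-group p-values.

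A retrospective detectable difference should not be added: it would rest on an assumed HA SD, and the confidence interval shows the precision achieved.

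The cost is wording and one interval, and the stated power becomes less favourable. The trial ran from July 2023 to May 2024 and the document is dated June 14, 2024, so resizing is not at issue and no extra enrolment is involved.

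### Choosing the study eye by its lower day-1 NIBUT, then measuring change from that same reading, can bias the within-arm NIBUT change upward; efficacy should rest on the between-group contrast

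*Combined protocol and SAP*

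**What the plan says.** Section 4 sets the visit schedule: "Patients were assessed at screening, baseline (day 1), and 2 follow-up visits", the latter at 3 and 6 months. Baseline is therefore the day-1 reading, separate from screening.

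Section 5 gives the eye rule for patients with two eligible eyes: "the eye with a lower baseline NIBUT was selected for the analyses", with the right eye taken in a tie. The same section defines the increment as last visit minus baseline, D = LV − B. Within arms, "The Friedman test (non-parametric) was performed to compare intra-group clinical outcomes"; between arms, "Inter-group clinical outcomes were analyzed with the Mann-Whitney U test", with the difference taken as the TriMix increment minus the HA increment. The significance level is 0.05.

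The sample size rests on a "statistically significant paired difference of 1.24 ± 2.56 s" within the TriMix arm. No primary endpoint or primary comparison is named.

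On measurement error, section 4.2 says that "the average of 3 consecutive measurements was calculated for statistical analysis". Section 2 also requires NIBUT below 10 s in at least one eye, both at screening and at randomization.

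**The concern.** The day-1 NIBUT does two jobs: it decides which eye is analysed, and it is the B that is subtracted from the outcome. An eye can be the lower of two because it is truly worse or because it happened to read low that day. The second part does not persist, so the chosen eye tends to read higher at later visits with no treatment effect. This is regression to the mean. It vanishes only if visit-to-visit error is zero or fully shared by the two eyes. Averaging three consecutive readings reduces noise within a session but not variation from day to day.

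The trial is sized on exactly this within-arm NIBUT change, and nothing in section 5 prevents a significant within-arm Friedman result from being presented as evidence that the product works. Part of such a rise can appear in both arms when neither product does anything.

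The scope is narrow. Only within-arm NIBUT is at issue; OSDI is a patient-level score and is not affected.

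**Working it through.** **The plan's own figure.** For a paired difference of 1.24 s with SD 2.56 s, two-sided 5% (sidedness is not stated) and 80% power: n = ((1.960 + 0.842) × 2.56 / 1.24)² = 33.5. Allowing for 20% dropout gives 33.5 / 0.8 = 41.8, or 33.5 × 1.2 = 40.1. The stated 40 per group is close to both, and 40 evaluable eyes give 86.5% power (normal approximation). The sizing is thus a within-arm calculation.

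**Formula for the spurious rise.** Let s² be the eye-specific visit-to-visit variance, v the variance of the true eye-specific level, and p the share of patients with two eligible eyes. From the expected minimum of two normal readings:

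rise = p × s² / √(π(s² + v))

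**Inputs.** The documents give none of s², v or p. Assumptions:
- If all the SD of 2.56 s for the change were visit noise, the variance per visit would be 2.56² / 2 = 3.277 (SD 1.81 s). This is a ceiling.
- Between 10% and 50% of that variance is specific to one eye, so s² = 0.328 to 1.638.
- 32 are analysed per arm (40 × 0.8).
- The Friedman test uses day 1, 3 months and 6 months; section 5 does not list the visits.

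Example (50% eye-specific, v = s², p = 1): 1.638 / √(π × 3.277) = 1.638 / 3.209 = 0.51 s.

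**Results.** Rise from the formula; Friedman rejection from 20,000 simulated trials with no true change (nominal 5%). Ranges run from 10% to 50% eye-specific.

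| v | p | Rise (s) | Friedman rejection |
|---|---|---|---|
| 9s² | 0.5 | 0.05 to 0.11 | 5.0% to 5.4% |
| 4s² | 0.5 | 0.07 to 0.16 | 5.0% to 5.8% |
| 4s² | 1 | 0.14 to 0.32 | 5.2% to 8.4% |
| s² | 0.5 | 0.11 to 0.26 | 5.3% to 7.5% |
| s² | 1 | 0.23 to 0.51 | 6.7% to 14.7% |
| 0, all noise eye-specific (limit) | 1 | 1.02 | 53.8% |

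**Sensitivity.**
- With 48 analysed in the larger arm (1.5 × 32), rejection is 5.7% to 6.7% (v = 4s², p = 0.5) and 7.8% to 21.7% (v = s², p = 1).
- Halving the noise variance with v held at the original s² (p = 1) gives 0.13 s and 6.0% at the 10% share, and 0.29 s and 11.6% at the 50% share.
- Adding screening as a fourth Friedman visit changes little: 6.3% and 14.6% (v = s², p = 1).

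**Controls.** With the eye not chosen on NIBUT, the rise is 0.000 s and rejection 4.9%. For the between-group Mann-Whitney test on change (48 vs 32, p = 1, five scenarios, 10,000 replicates), rejection is 4.7% to 5.3% and the mean difference −0.013 to 0.006 s. The bias cancels there.

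**The case against.** The strongest reply is that the randomized comparison is sound and already in section 5. The eye rule is fixed before treatment and is the same in both arms, and nowhere do the documents say that a within-arm result will be taken as efficacy. Resting efficacy on the between-group contrast would be right whichever eye was chosen, since within-arm change also carries natural history, washout and placebo response. On this view the real gap is the unnamed primary comparison. That is fair as to the remedy. But the eye rule is a specific, avoidable source of bias written into the plan, and the only sizing uses the quantity it biases.

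Second, the 10 s entry limit produces regression to the mean by itself. With it modelled (assumed mean NIBUT 6 or 8 s, person SD 2 s), the limit alone gives about 0.1 to 0.34 s, and choosing the lower eye adds about 0.1 to 0.4 s more. The eye rule is therefore not the only source, and in some settings not the larger one. This strengthens the caution about within-arm tests.

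Third, the size is undetermined. With half of patients bilateral and v at least 4s², rejection stays between 5.0% and 5.8%; above 10% at 32 per arm requires every patient to be bilateral and v no larger than the original s². This stands.

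Fourth, the formula assumes normal readings, while section 5 reports that the endpoints were not normal. The seconds and percentages depend on that assumption. The direction does not: a low error always makes an eye more likely to be chosen.

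**Conclusion.** The concern holds. As written, the eye rule can bias the within-arm NIBUT change upward and raise the error rate of the within-arm Friedman test, and nothing else in the plan corrects for it. The between-group comparison is not biased.

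The direction is secure unless visit error is nil or wholly shared between eyes. The size cannot be determined from the documents. Over the assumed range (normal readings, 10% to 50% of a ceiling visit variance eye-specific, v from s² to 9s², half or all patients bilateral, 32 analysed) the rise is 0.05 to 0.51 s, or 4% to 41% of the 1.24 s planning effect (0.05 / 1.24 and 0.51 / 1.24), with false-positive rates of 5.0% to 14.7%. The limit of 1.02 s and 53.8% is a bound, not an expectation. The point should be addressed because the remedy is cheap; it does not undermine the trial's randomized result.

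**What to change.** In section 5, state that efficacy conclusions rest on the between-group difference in change already defined there (TriMix increment minus HA increment, Mann-Whitney), and that within-arm NIBUT changes are reported descriptively, without significance claims.

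The protocol is dated June 14, 2024, after the stated study period of July 2023 to May 2024, so this wording governs interpretation and cannot count as pre-specification.

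**Cost.** No new data or analysis is needed. The within-arm NIBUT significance claim is given up, and the remaining contrast is one the trial was not sized for. If the between-group difference were the full 1.24 s with SD 2.56 s (an assumption; the documents give none), simulated Mann-Whitney power is about 53% with 48 vs 32 analysed. It is about 45% with 38 vs 26, which is 80 randomized 1.5:1 as 48 and 32, each less 20%. That reflects the sizing and is no reason to rely on the biased contrast.

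**Optional.** If both eyes' NIBUT was recorded at screening, add a sensitivity analysis, labelled post hoc, that selects the eye on the screening reading. That reading may precede the one-month washout. The eye it picks would not be the lower one on day 1 in about 20% (v = 4s²) to 33% (v = s²) of bilateral patients, from arccos(v / (v + s²)) / π. The 10 s limit at randomization would still leave about 0.11 to 0.32 s (v = s², assumed means 6 to 8 s, person SD 2 s), so this does not replace the main change.

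### The only within-arm test named (Friedman) does not test the increment the plan defines, and the stated power was calculated for a different, paired test

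*Combined protocol and SAP*

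**What the plan says.** All of the statistical text is in Section 5.

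- **Sizing.** The calculation uses a "paired difference of 1.24 ± 2.56 s at 2 months after the TriMix tear substitute treatment onset". Its source is given as follows: "This assumed difference was based on the findings of a pilot study with 25 eyes". From this, "a sample size of 40 eyes per group would yield a power" above 80%, with a 20% discontinuation rate taken into account.
- **Within-arm effect.** An increment is calculated in each group: "It was defined as the change from the last visit (LV) to baseline (B"), with the formula LV − B.
- **Within-arm test.** "The Friedman test (non-parametric) was performed to compare intra-group clinical outcomes". No paired test, no follow-up contrast of last visit against baseline, and no list of the visits entered is given.
- **Between-arm test.** Mann-Whitney U, with the group difference formed from the two increments.
- **Significance.** "A P value of less than 0.05 is considered to be statistically significant". Sidedness is not stated.

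Section 4 (Clinical outcomes) gives the visits: "Patients were assessed at screening, baseline (day 1), and 2 follow-up visits", at 3 and 6 months.

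**The concern.** Three things that should line up do not. The sample size rests on a contrast between two time points. The reported effect is also such a contrast. The named test asks a different question: whether any visit differs from any other, using only the rank order of each patient's readings.

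Two consequences follow. First, a reader who wants a P value for the within-arm increment will find only the Friedman one, and it can be significant when the increment is zero. Second, the quoted power belongs to a test that the plan does not name. Neither problem comes from dropout; both would arise with complete data.

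**Working it through.** **Inputs.** Difference 1.24 s, SD 2.56 s, 40 eyes, 20% discontinuation and the 0.05 level come from Section 5; the visits come from Section 4. Assumptions: a two-sided test; 2.56 s is the SD of the paired difference; the endpoint is NIBUT (inferred from the unit); the 2-month pilot effect applies at month 6; last visit means month 6.

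**Step 1: reproduce the plan's figure.** Paired formula:

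n = [(1.960 + 0.842) × 2.56 / 1.24]² = 33.45, so 34 eyes for 80% power.

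33.45 × 1.2 = 40.1, which matches the stated 40. The 40 therefore appears already to include the dropout allowance.

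Power = Φ(1.24√n / 2.56 − 1.960):

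- n = 40: Φ(3.063 − 1.960) = 86.5% (84.8% by noncentral t)
- n = 32 (40 × 0.8): Φ(2.740 − 1.960) = 78.2% (75.6% by noncentral t)

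So the figure above 80% is right for a paired test on 40 analysed eyes.

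**Step 2: power of Friedman for the same effect.** Simulation with 20,000 trials per scenario, complete data, baseline / month 3 / month 6, and SD(month 6 − baseline) fixed at 2.56 s. Friedman is referred to chi-square on 2 df; the signed-rank test uses the normal approximation. Error shape, correlation and time profile are assumptions, because the documents give none of them. With no change at any visit, both tests reject in about 5% of trials. Results at 40 eyes:

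| Visit errors | Friedman, full gain by month 3 | Friedman, linear rise | Signed-rank, month 6 − baseline | Friedman, change at month 3 only |
|---|---|---|---|---|
| Normal, independent | 75% | 62% | 83% | 75% |
| Normal, autoregressive (0.5) | 83% | 67% | 83% | 92% |
| Normal, adjacent-visit SD 2.2 s | 81% | 66% | 83% | 89% |
| Normal, adjacent-visit SD 1.85 s | 88% | 71% | 83% | 98% |
| Exponential | 95% | 91% | 92% | 97% |
| t, 3 df | 96% | 89% | 95% | 95% |
| Lognormal, log-SD 0.75 | 98% | 96% | 96% | 99% |

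Milder departures from normality: lognormal errors with log-SD 0.5 gave Friedman 90% (full gain) and 82% (linear), against 90% for signed-rank. Laplace errors gave Friedman 89% and 80%.

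At 32 eyes Friedman gives 50–65% with independent normal errors and 80–92% with exponential or t errors. Signed-rank with normal errors gives about 76% at 34 eyes and about 74% at 32.

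**Step 3: a change that does not last.** The last column sets the mean change at 1.24 s at month 3 and zero at month 6. Friedman rejects in 75% or more of trials under every shape shown, while the signed-rank test of month 6 − baseline stays at about 5%. With a transient change of half that size (0.62 s), Friedman rejects in 24–52%.

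**Step 4: if only baseline and last visit are entered.** Friedman then reduces to a sign test. The chance that a patient's change is positive is Φ(1.24 / 2.56) = 0.686, and power at 40 eyes is about 63% with normal errors. This reading does test a baseline-to-last-visit change, but it is still not the test behind the sample size.

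**The case against.** **The plan never says that the Friedman P value judges the increment.** This is correct. A reader might infer that the plan treats a significant Friedman result as a significant increment, but the text does not say so. The increment is calculated and then carried into the between-arm difference. What remains is a reporting risk, because no other within-arm test is named. The visits entered are also inferred.

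**Full reversal by month 6 is an extreme case.** Dosing continues for 6 months and nothing in the documents suggests such a course. The scenario shows what the test responds to; it does not predict the result.

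**The power shortfall depends on normal errors.** This stands. Section 5 reports that the endpoints failed a normality check. Under the skewed or heavy-tailed shapes tried, Friedman power at 40 eyes is about 80% or higher. A reader might infer that the trial misses its stated power; the documents do not support that. Nor is signed-rank always the stronger test: for a sustained gain, Friedman reached 88% against 83% in one correlated normal scenario and 98% against 96% in one skewed scenario.

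**Friedman is a standard choice for three repeated non-normal measurements, and the comparison that matters is between arms.** Both are true, and they limit the severity. Neither gives the increment a test of its own.

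**Conclusion.** The mismatch holds. The powered contrast and the reported contrast are both two-time-point differences, and the one within-arm test named is neither the paired test used for sizing nor, over three visits, a test of last visit minus baseline.

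If the P value is nevertheless read beside the increment, a 1.24 s change confined to month 3 would look significant in about 75% to 95% or more of trials at 40 eyes, against about 5% for a direct test. This assumes that three visits are entered and that SD(month 6 − baseline) is 2.56 s.

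On power, the supportable conclusion is that the figure above 80% was calculated for a paired test and is unverified for Friedman. At 40 eyes Friedman gives 62–75% with independent normal errors, 67–83% with autoregressive normal errors, and mostly 82–95% (extremes about 80% and 98%) with skewed or heavy-tailed errors. A shortfall is possible but not established.

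Severity is minor to moderate. The Mann-Whitney comparison between arms is untouched. That the sizing is within-arm while the randomized comparison is between arms is a separate matter.

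**What to change.** Add to Section 5:

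> Within each arm, the month-6 minus baseline change is tested with the Wilcoxon signed-rank test and reported as the Hodges-Lehmann median change with 95% CI; month 3 minus baseline is shown the same way. The Friedman test over baseline, month 3 and month 6 is descriptive, and its P value is not attached to the increment.

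State that the power figure refers to this within-arm paired contrast, not to Friedman and not to the between-arm comparison. Quote it twice, under normal errors: for 40 analysed eyes (about 83% signed-rank, 85% paired t) and for the eyes expected after dropout (signed-rank about 76% at 34, about 74% at 32). Note that error shape changes these figures, and say how the 20% allowance was applied.

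The document is dated June 14, 2024, after the stated study period ending in May 2024, and reports the normality test as already done. If data have been seen, label the change as post hoc.

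The cost is a few sentences and one standard procedure on data already collected. The downsides are that the omnibus test becomes descriptive and that the quoted power after dropout is less favourable than the current statement.
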